3.4.2 Optional Second Treatment Course Calendar

Evaluation	Pre Therapy ¹	First Cycle		Second and Third Cycles		Fourth and Later Cycles	Post Therapy	
		Day 1	Day 15	Day 1	Day 15		Day 1	Day 29 Final Cycle
History and physical ²	X	X	X	X		X	X	X
Clinical Labs ¹	X	X	X	X	X	X	X	X
Pregnancy Test ³	X	X	X	X		X	X	X
Pomalidomide Education and Counseling ⁴	X	X		X		X		
HIV Western blot	X							
Chest X-ray	X							
Electrocardiogram	X							
KS Response Evaluation:								
KS Tumor Measurements	X			X		X	X	
KS Tumor Photography ⁵	X			X		X	X	
KS Non-invasive Tumor Imaging ⁵	X			X		X	X	
Tumor Biopsies ⁶		Not performed for second course						
Quality of Life Assessment ⁷	X					X		X
Pharmacokinetics ⁸		Not performed for second course						
Adverse Event Monitoring		X						X
KSHV VL (PBMCs and saliva), viral IL-6, human cytokines ⁹		X		X		X	X	
KSHV Immune Response Assays ¹⁰	X							X
Monocyte and T cell activation and subsets ¹⁰	X					X		X
HIV VL (Single Copy Research Assay) ¹¹	X	X		X		X	X	X

¹ Pre-therapy studies will be performed at least 2 days before commencement of second course of therapy.

² Includes current medications and ECOG performance status

³ In females of child-bearing potential (FCBP), as defined in [Appendix 1](#). Urine and serum β -HCG will be performed within 14 days prior to starting pomalidomide, again within 24 hours of starting pomalidomide, and then performed weekly for the first 28 days of study participation and then every 28 days while on study, at study drug discontinuation, and at day 28 following study drug discontinuation. If menstrual cycles are irregular, the pregnancy testing must occur weekly for the first 28 days and then every 14 days while on study, at study discontinuation, and at days 14 and 28 following study drug discontinuation.

⁴ All patients must be counseled about pregnancy precautions, risks of fetal exposure and other risks. The counseling must be done on Day 1 of each cycle (or at a minimum of every 28 days) and at drug discontinuation. See [Appendix 1](#): Pomalidomide Risks of Fetal Exposure, Pregnancy Testing Guidelines and Acceptable Birth Control Methods and: [Appendix 2](#) Pomalidomide Education and Counseling Guidance Document.

⁵ Pre-therapy, day one of subsequent cycles until the sixth cycle and then (for patients receiving more than six cycles) day one of odd-numbered cycles (beginning with Cycle 7) and again at the end of second course of therapy.

⁶ Research biopsies will not be performed for subjects receiving a second course of therapy.

⁷ Pre-therapy, day one of cycle four, and end of second course of therapy.

⁸ Pharmacokinetics will not be performed for subjects receiving a second course of therapy.

⁹ At each collection: 1 yellow top tube for PBMCs; 1 blue top tube for saliva; 2 red top tubes for viral IL-6; 3 green top tubes for cytokines; 2 yellow top tubes for storage

¹⁰ Repeated day one of cycle four and 28±7 days following the end of second course of therapy.

¹¹ Only in HIV infected subjects whose HIV VL is undetectable by conventional assays.

As noted in Section [3.2.1.5](#), treatments and corresponding evaluations may be rescheduled to the closest day possible without constituting a protocol violation (e.g. for Federal holidays or unforeseen circumstances such as travel difficulties, snow closures and the like).

3.4.3 Baseline Studies

Screening clinical laboratory and radiographic studies may be used for baseline evaluation provided they were obtained within 14 days of study enrollment or within 28 days of first dose of therapy, *except* baseline CBC and acute care, mineral and hepatic panel and (for females) a pregnancy test is required within 24 hours prior to first dose of therapy. CBC, acute care, mineral and hepatic panels, and pregnancy test repeated within 24 hours of first dose must continue to meet eligibility criteria (Sections [2.1.1.8](#) to [2.1.1.10](#)) for the subject to commence therapy.

Pharmacokinetics studies must be performed day one of cycle one. Correlative studies must be performed pre-therapy (for Immune Activation and KSHV Immune Response Assays) or day 1 of cycle one (for Cytokine, Angiogenesis and Virologic Studies) as specified in Section [5.1.2](#).

3.4.3.1 Clinical Examination

3.4.3.1.1 Complete medical history

3.4.3.1.2 Comprehensive physical examination

3.4.3.2 Clinical Laboratory Data

3.4.3.2.1 CBC with differential and reticulocyte count

- 3.4.3.2.2 Acute care panel (Sodium, Potassium, Chloride, CO₂, Creatinine, Glucose, and Urea Nitrogen)
- 3.4.3.2.3 Mineral panel (Phosphorus, Magnesium, Albumin, and Calcium)
- 3.4.3.2.4 Hepatic panel (Alkaline Phosphatase, ALT, AST, Total Bilirubin, and Direct Bilirubin)
- 3.4.3.2.5 C-reactive protein
- 3.4.3.2.6 Creatine kinase, uric acid, LDH, amylase and lipase
- 3.4.3.2.7 Thyroid stimulating hormone (TSH)
- 3.4.3.2.8 APTT, PT, thrombin time (TT), fibrinogen, D-dimer
- 3.4.3.2.9 Lymphocyte phenotype TBNK (requires simultaneous CBC and automated differential)
- 3.4.3.2.10 HIV viral load if HIV seropositive by Western Blot
- 3.4.3.2.11 EBV viral load if seropositive
- 3.4.3.2.12 CMV viral load if seropositive
- 3.4.3.2.13 Hepatitis A antibody screen
- 3.4.3.2.14 Hepatitis B antibody screen (HBV S Ag, HBV S Ab, HBV core Ab) and viral load if there is evidence of past or current infection
- 3.4.3.2.15 Hepatitis C antibody screen and HCV viral load
- 3.4.3.2.16 RPR
- 3.4.3.2.17 Tuberculosis testing by PPD or interferon gamma release assay (Quantiferon Gold)

3.4.3.3 Pregnancy Testing

- 3.4.3.4 Urine and serum β-hCG (female subjects only)

3.4.3.5 Electrocardiogram (EKG)

3.4.3.6 Pharmacokinetic Studies (see Section 5.1.1)

3.4.3.7 Correlative Studies (see Section 5.1.2)

3.4.3.8 Baseline assessment for response evaluation (see Sections 6.2.1 and 6.2.2)

3.4.4 Treatment Phase Studies

Clinical examination and clinical laboratory evaluation will be repeated each cycle, except for additional clinical assessment on day 15 of cycle one and additional laboratory toxicity checks on day 15 of cycle one, two and three (see Section 3.4). Laboratory toxicity checks may be performed by the patient's primary care physician through a certified outside laboratory with results to be provided to NCI investigators, for patients living at a distance from the Clinical Center.

3.4.4.1 Clinical Examination

Evaluation will be repeated on or immediately before day 1 of each cycle, and on day 15 of cycle 1. Objective signs, relevant positive and negative findings on history and examination, and clinical toxicities will be evaluated and recorded each visit.

3.4.4.2 Clinical Laboratory Data

- 3.4.4.2.1 Evaluations will be repeated on or immediately before day 1 of each cycle.

- 3.4.4.2.2 CBC with differential and reticulocyte count
- 3.4.4.2.3 Acute care panel (Sodium, Potassium, Chloride, CO₂, Creatinine, Glucose, and Urea Nitrogen)
- 3.4.4.2.4 Mineral panel (Phosphorus, Magnesium, Albumin, and Calcium)
- 3.4.4.2.5 Hepatic panel (Alkaline Phosphatase, ALT, AST, Total Bilirubin, and Direct Bilirubin)
- 3.4.4.2.6 C-reactive protein
- 3.4.4.2.7 Creatine kinase, uric acid, LDH, amylase and lipase
- 3.4.4.2.8 Thyroid stimulating hormone (TSH)
- 3.4.4.2.9 APTT, PT, thrombin time (TT), fibrinogen, D Dimer
- 3.4.4.2.10 HIV viral load if HIV seropositive
- 3.4.4.2.11 Lymphocyte phenotype TBNK (requires simultaneous CBC and automated differential)
- 3.4.4.2.12 EBV viral load if seropositive
- 3.4.4.2.13 CMV viral load if seropositive
- 3.4.4.2.14 HBV viral load if evidence of past or current infection
- 3.4.4.2.15 HCV viral load if evidence of past or current infection.

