- 3.1.2.2.5 Grade 4 creatine kinase (CK) elevations will not be considered dose-limiting if it is determined that this is at least possibly due to recent exercise or trauma. This is because it is our experience that some KS patients and HIV-infected patients on clinical trials develop substantially increased CK levels from exercise or trauma.
- 3.1.2.3 **Any grade 3 toxicity** that is at least possibly due to pomalidomide and is not attributable to HIV, its therapy, or KS with the following restrictions:
 - 3.1.2.3.1 Those toxicities excluded above in section **3.1.2.2**
 - 3.1.2.3.2 Grade 3 thrombocytopenia will only be considered dose limiting if grade 3 for 14 days or more (all grade 4 thrombocytopenia will be considered dose limiting).
 - 3.1.2.3.3 Grade 3 asymptomatic hyperuricemia or hypophosphatemia will not be considered dose limiting, as these are often caused by HIV infection or antiretroviral therapy.
 - 3.1.2.3.4 Grade 3 amylase elevations will not be considered dose-limiting if it is determined that it is not of pancreatic origin.
 - 3.1.2.3.5 For rash, grade 3 toxicity is considered dose-limiting only if it does not decrease to grade 1 within 4 weeks off therapy; if it recurs on re-challenge with pomalidomide; or if it is erythema nodosum characterized by a desquamating rash.
 - 3.1.2.3.6 For hypertension, grade 3 toxicity is considered dose limiting where systolic blood pressure of ≥ 160 mm Hg or diastolic blood pressure of ≥ 100 mm Hg is not controlled with antihypertensive medications (all grade 4 hypertension will be considered dose limiting).
- 3.1.2.4 Any arterial or deep venous thrombembolic event or a second superficial thromboembolic event that is at least possibly due to pomalidomide.
- 3.1.2.5 Inability to deliver pomalidomide on at least 50% of scheduled days during the first two cycles of therapy as a result of toxicity that is probably or definitely attributable to pomalidomide will be considered dose limiting. Delivery interruptions not related to pomalidomide (for example, due to unrelated intercurrent illness, patient personal emergencies, or other exigencies) will not be considered for this criterion.

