3.1.3 Dose De-escalation

Up to six subjects will initially be treated with pomalidomide at dose level 1, 5mg PO daily for 21 days followed by 7 days 'rest' to complete the 28 day cycle. Subject to toxicity evaluation (Section **3.1.2**), this dosage may be deescalated to dose level minus 1, 3mg PO daily for 21 days followed by 7 days 'rest' to complete the 28 day cycle in a second cohort of up to six subjects.

A dose will be considered as toxic if two or more of the subjects entered at that dose level develop a DLT within the first 8 weeks (2 cycles) of drug administration. This time period has been selected, in line with prior HAMB studies, as in the great majority of cases KS will require

at least 8 weeks of treatment. The tolerated dose will be defined as the highest dose level administered as part of the protocol where 0 or 1 of 6 subjects experience a dose limiting toxicity within the first 8 weeks of drug administration.

If it is determined that a dose is toxic then subjects in that group who have not experienced a DLT or off-therapy criterion will be dropped to the next lower level. In the case that the lowest predetermined dose is determined to be toxic, all subjects will cease therapy unless in the interim the protocol has been amended by seeking IRB approval to include an additional lower dose level.

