Infection at any site (\geq CTCAE Grade 3) at least possibly attributable to pomalidomide	Suspend or hold Pomalidomide.	On or after day 29 and following documentation of resolution to \leq CTCAE Grade 1 at the same dose level. Therapy may resume during oral antibiotic consolidation therapy if there is no clinical or laboratory evidence of active infection.
CK elevation at least possibly attributable to pomalidomide (\geq CTCAE Grade 3)	Hold pomalidomide for a maximum of 2 weeks. Encourage increased oral fluid intake and avoidance of strenuous physical activities. Administer intravenous fluid if CK $>10,000$ U/L.	Resume therapy at the same dose level once resolution to \leq CTCAE Grade 2. Permanently discontinue if not at \leq CTCAE Grade 2 after a total of 3 weeks off drug (including the time off drug during the last week of the cycle) or if CK rises again to grade 4 and it is not possibly attributable to excess exercise or to trauma.
Any other DLT of CTCAE Grade 3 at least possibly attributable to pomalidomide	Suspend or hold pomalidomide.	On or after day 29 and following resolution to \leq CTCAE Grade 1 at the same dose level (see Section 3.5).

Event	Action	Resumption of Therapy
Any other DLT of CTCAE Grade 4 at least possibly attributable to pomalidomide	Discontinue therapy.	Not to resume (see section 3.3).

*At the discretion of the investigators, subjects who experience grade 3 or 4 neutropenia requiring G-CSF during a cycle as described below may receive G-CSF 5mcg/kg/daily SC rounded by $\pm 10\%$ to use the most economical combination of available products during the 'rest' days of subsequent cycles to minimize recurrent neutropenia.

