3.4 STUDY CALENDAR

3.4.1 Initial Treatment Course Calendar

Evaluation	Screen	Pre Therapy ¹	First Cycle		Second and Third Cycles		Fourth and Later Cycles	Post Therapy	
			Day 1	Day 15	Day 1	Day 15		Day 1	Day 29 Final Cycle
History and physical ²	X		X	X	X		X	X	X
Clinical Labs ³	X		X	X	X	X	X	X	X
Pregnancy Test ⁴	X		X	X	X		X	X	X
Pomalidomide Education and Counseling ⁵		X	X		X		X		
HIV Western blot	X								
Chest X-ray	X								
Electrocardiogram	X								
KS Response Evaluation									
KS Tumor Measurements		X			X		X	X	
KS Tumor Photography ⁶		X			X		X	X	
KS Non-invasive Tumor Imaging ⁶		X			X		X	X	
Tumor Biopsies ⁷	X				X			X	
Quality of Life Assessment ⁸		X					X		X
Pharmacokinetics ⁹			X	X					
Adverse Event Monitoring			X						X
KSHV VL (PBMCs and saliva), viral IL-6, human cytokines ¹⁰			X		X		X	X	
KSHV Immune Response Assays ¹¹		X							X
Monocyte and T cell activation and subsets ¹¹		X					X		X
HIV VL (Single Copy Research Assay) ¹²		X	X		X		X	X	X

¹ Pre-therapy studies will be performed after screening and enrollment, and at least 48 hours before commencement of therapy.

² Includes current medications and ECOG performance status

³ See Section 2.2.2 for screening labs, 3.4.3 for baseline labs, 3.4.4 for on treatment labs and 3.4.5 for post treatment labs. Note as described in Section 3.4.4, day 8, 15 and 22 of cycle 1 and Day 15 of cycles 2 and 3 are limited laboratory toxicity checks only. Laboratory toxicity checks may be performed by the patient's primary care physician through a certified outside laboratory with results to be provided to NCI investigators, for patients living at a distance from the Clinical Center.

⁴ In females of child-bearing potential (FCBP), as defined in [Appendix 1](#). Urine and serum β -HCG will be performed within 14 days prior to starting pomalidomide, again within 24 hours of starting pomalidomide, and then performed weekly for the first 28 days of study participation and then every 28 days while on study, at study drug discontinuation, and at day 28 following study drug discontinuation. If menstrual cycles are irregular, the pregnancy testing must occur weekly for the first 28 days and then every 14 days while on study, at study discontinuation, and at days 14 and 28 following study drug discontinuation.

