3.4.4.3 Additional Clinical Laboratory Toxicity Check

- 3.4.4.3.1 Evaluations will be repeated on day 15 of cycles one, two and three only. Results from these evaluations will be used to determine if dose adjustments are required for *subsequent* days of the cycle (as outlined in **Table 1**).
- 3.4.4.3.2 CBC with differential and reticulocyte count
- 3.4.4.3.3 Acute care panel (Sodium, Potassium, Chloride, CO₂, Creatinine, Glucose, and Urea Nitrogen)
- 3.4.4.3.4 Mineral panel (Phosphorus, Magnesium, Albumin, and Calcium)
- 3.4.4.3.5 Hepatic panel (Alkaline Phosphatase, ALT, AST, Total Bilirubin, and Direct Bilirubin)

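### After the first dose, CK, amylase and lipase are scheduled only after the rest week, so brief, silent rises on drug can be missed

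*Combined protocol and SAP*

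**What the plan says.** - **Dosing (3.1.3).** Dose level 1 is "5mg PO daily for 21 days followed by 7 days 'rest' to complete the 28 day cycle". The 3 mg level has the same pattern.
- **Full panel (3.4.4.2).** The timing rule is "Evaluations will be repeated on or immediately before day 1 of each cycle". The list includes "Creatine kinase, uric acid, LDH, amylase and lipase". The same tests are drawn at screening, at baseline and at the two post-treatment visits (2.2.2, 3.4.3.2, 3.4.5).
- **Mid-cycle check (3.4.4.3).** "Evaluations will be repeated on day 15 of cycles one, two and three only". It consists of blood counts and the acute care, mineral and hepatic panels. On its purpose, the section says "Results from these evaluations will be used to determine if dose adjustments are required for" later days of the same cycle, with reference to Table 1.
- **Calendar footnote 3 (3.4.1).** It gives different days: "day 8, 15 and 22 of cycle 1 and Day 15 of cycles 2 and 3 are limited laboratory toxicity checks only".
- **DLT rules (3.1.2).** Grade 4 CK can be a DLT unless exercise or trauma is a possible cause. For amylase, "Grade 3 amylase elevations will not be considered dose-limiting if it is determined that it is not of pancreatic origin". Lipase is not named and enters only through the general grade 3 and grade 4 rules.
- **Table 1 (3.3).** CK of grade 3 or higher that may be due to the drug has its own row: a hold of at most 2 weeks, and permanent discontinuation if CK has not recovered after 3 weeks off drug, "including the time off drug during the last week of the cycle".

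**The concern.** Safety and tolerability are the primary objective (1.1.1). Two tests named in the DLT rules, one of which also has its own Table 1 row, are scheduled only once the patient has been off drug for about a week. The mid-cycle check falls on a dosing day and is meant to inform Table 1 decisions, yet it leaves these tests out.

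A rise that appears during dosing, causes no symptoms and fades in the rest week would enter neither the DLT count nor the toxicity tables, and would not prompt the CK row. Such misses all act in one direction: they make the drug look better tolerated. The rules remain in force after phase I. Table 1 covers phase 2 and the second course (3.3), the off-therapy criteria use the DLT definitions (3.6.1), and the second course follows the first (3.1.6.5).

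**Working it through.** The plan gives no figure to reproduce here, so the check is a map of dosing days against blood draws.

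**Inputs.** 21 dosing days per 28-day cycle (3.1.3); DLT window of 8 weeks, study days 1-56 (3.1.2); panel contents and days (3.4.4.2, 3.4.4.3); pomalidomide half-life 8.2-10.8 h (1.2.3.3).

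**Dosing days in the window.** Days 1-21 and 29-49, which is 2 × 21 = 42 days.

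**Scheduled draws after the first dose, on the days given in 3.4.4:**

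| Study day | Cycle day | Position | Counts, acute care, mineral, hepatic | CK, amylase, lipase |
|---|---|---|---|---|
| 15 | cycle 1 day 15 | dosing | yes | no |
| 29 | cycle 2 day 1 | 29 − 21 = 8 days after last dose | yes | yes |
| 43 | cycle 2 day 15 | dosing | yes | no |
| 57 | cycle 3 day 1 | 57 − 49 = 8 days after last dose | yes | yes, but outside days 1-56 unless drawn early |

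CK and amylase draws within the dosing stretch after day 1 (days 2-21) of either cycle: 0, against 2 for the other panels. The window therefore holds one certain post-dose CK and amylase value, on day 29.

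**Drug remaining at the draw.** 8 days = 192 h. 192 / 10.8 = 17.8 and 192 / 8.2 = 23.4 half-lives, so less than 0.001% remains.

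**Marker remaining at the draw.** The documents give no rate of decline for CK or amylase. Assume a half-life h of 24-72 h. The fraction of the end-of-dosing excess left is 0.5^(192/h):
- h = 24: 0.5^8 = 0.4%
- h = 36: 0.5^5.33 = 2.5%
- h = 72: 0.5^2.67 = 16%

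If the sample is taken one day before day 1 (168 h), the range is 0.5^7 = 0.8% to 0.5^2.33 = 20%. The conclusion is the same.

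**Table 1 CK clock.** With detection on day 1, 1 rest week + a hold of up to 2 weeks = 3 weeks, which equals the discontinuation limit. With detection on day 15, a 2-week hold runs to day 15 + 14 = 29 and already contains the rest week, while 3 weeks off drug runs to day 15 + 21 = 36. The row fits day 1 detection. It would need clarifying if CK were also measured on day 15.

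**The case against.** The best defence is that the short mid-cycle panel is a reasonable choice. The clinical summary (1.2.3.4) names blood toxicity and deep venous thrombosis as the main serious events and reports no CK, amylase or lipase signal. Sustained rises would still show on day 1, and symptomatic ones can surface at clinical visits, including day 15 of cycle 1. No event rate is available, and the size of any bias rests on an assumed half-life. All of this stands, and it limits the point to transient, asymptomatic rises.

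It can also be said that 3.4.4.3 does not promise to test every Table 1 row, since the thrombosis and infection rows are not laboratory rows. That is true, but CK is the one named laboratory row that the check cannot inform; the others rest on blood counts, which it includes.

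A reader might infer four stronger things that the documents do not support:
- **That these tests are never drawn on a dosing day.** Day 1 is a dosing day. What holds is that each value after the first dose follows the rest period.
- **That all three tests feed both sets of rules.** Only CK has its own Table 1 row, lipase is in no named rule, and 3.1.2.3.1 removes CK from the grade 3 DLT rule.
- **That the CK row contradicts the schedule.** Its clock fits detection on day 1.
- **That the phase I conclusion is wrong.** Nothing shows that an event was missed.

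**Conclusion.** The point holds as a gap in ascertainment. No CK or amylase value is scheduled within days 2-21 of any cycle, the DLT window has one certain post-dose value, and the day 15 check lacks the CK that one Table 1 row needs. The direction is known, because missed events can only favour tolerability. The size is not: the 0.4%-16% range assumes a marker half-life of 24-72 h and a draw 8 days after the last scheduled dose. The effect on the 2-of-6 rule cannot be computed without a true rate of CK or amylase DLTs and the share detected, and the documents give neither.

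Practical reach is limited. Dose selection closed with no DLTs in the first six patients (3.1.5), and 10.4 foresees at most three more subjects in each cohort after amendment G. A new test cannot recover past values, so the phase I result can only be qualified. The change is still worth making for any remaining first-course or second-course treatment.

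**What to change.** 1. Add CK and amylase, with lipase to help judge pancreatic origin, to the day 15 panel in 3.4.4.3 for both treatment courses. Values taken during dosing in the DLT window go from 0 to 2 (days 15 and 43), with a third in cycle 3 (day 56 + 15 = 71).
2. Have the study team reconcile that panel with its stated purpose, with footnote 3 of the 3.4.1 calendar (days 8, 15 and 22 of cycle 1, against day 15 only in 3.4.4.3), and with the off-drug clock in the Table 1 CK row. How that clock should run after mid-cycle detection is the team's decision; no clinical rule is proposed here.
3. Report the 0-of-6 DLT result, and the CK and amylase toxicity rates, with a statement that these tests were scheduled only after the rest week. If treatment is complete or the panel is not changed, this step alone applies.

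**Cost.** Blood is already drawn on day 15, so no visit is added. There is a small laboratory cost, including at the outside laboratories that 3.4.4 allows, and some incidental CK rises from exercise will be found, for which 3.1.2.2.5 already has a DLT exception.

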3.4.4.3 Additional Clinical Laboratory Toxicity Check

- 3.4.4.3.1 Evaluations will be repeated on day 15 of cycles one, two and three only. Results from these evaluations will be used to determine if dose adjustments are required for *subsequent* days of the cycle (as outlined in **Table 1**).
- 3.4.4.3.2 CBC with differential and reticulocyte count
- 3.4.4.3.3 Acute care panel (Sodium, Potassium, Chloride, CO₂, Creatinine, Glucose, and Urea Nitrogen)
- 3.4.4.3.4 Mineral panel (Phosphorus, Magnesium, Albumin, and Calcium)
- 3.4.4.3.5 Hepatic panel (Alkaline Phosphatase, ALT, AST, Total Bilirubin, and Direct Bilirubin)

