In the phase 1b study in 24 patients with relapsed or refractory multiple myeloma([119](#)), 24 patients received a dose-escalating regimen of oral pomalidomide, administered continuously with arbitrarily defined 28 day cycles and commencing at a dose of 1mg daily (escalated to 2, 5, and 10mg). Dose limiting toxicities were assessed during the first four weeks of therapy. The most common drug-related toxicity was neutropenia, with grade 3/4 neutropenia occurring in 14 patients overall and increasing in a dose dependent manner. One deep venous thrombosis was observed in the DLT assessment timeframe, though this was probably due to unrelated melanoma developing in a groin lymph node, and three additional subjects developed thromboses after 4, 9 and 11 months of therapy respectively. No other severe (grade 3/4) non-hematologic toxicity was observed. Hematologic toxicity was less severe after the initial cycle, with the median time to grade 3/4 neutropenia in those experiencing this event being 3 weeks on therapy. The maximum tolerated dose in this population was 2mg daily continuous dosing.

A second arm of the phase 1b study (reported separately([132](#))) utilized the same dose levels (1mg escalated to 2, 5, and 10mg) but in an alternate-daily dosing schedule, again continuously for a 28 day 'cycle'. A further 24 patients were enrolled. The most common drug-related toxicity was again neutropenia, which was grade 3 in 6 of 17 patients (35%) treated at or below the 5mg dose level (with no grade 4 toxicity at these levels), and grade 4 in three patients, all at the 10mg alternate daily dose level. No other serious possibly drug-related adverse events were reported. The maximum tolerated dose in this population was therefore 5mg alternate daily.

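### Footnote 3 of the initial-course calendar puts cycle 1 laboratory toxicity checks on days 8, 15 and 22, but Section 3.4.4, which it cites, gives day 15 only

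*Combined protocol and SAP*

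**What the plan says.** Four places describe the cycle 1 laboratory checks.

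- Section 3.4.1, footnote 3, cross-refers to the treatment-phase text: "Note as described in Section 3.4.4, day 8, 15 and 22 of cycle 1". It classes these, with day 15 of cycles 2 and 3, as limited laboratory toxicity checks.
- Section 3.4.4, the text cited, provides for "additional laboratory toxicity checks on day 15 of cycle one, two and three". It mentions neither day 8 nor day 22.
- Section 3.4.4.3.1 gives the same days and closes the list: "Evaluations will be repeated on day 15 of cycles one, two and three only".
- The grid in Section 3.4.1, as it can be read from the extracted table, has only Day 1 and Day 15 columns for the first cycle.

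For the full panel, Section 3.4.4.2 says: "Evaluations will be repeated on or immediately before day 1 of each cycle". After day 15 of cycle 1, the next count under Section 3.4.4 is therefore day 29.

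The second-course calendar (Section 3.4.2) shows days 1 and 15 for cycle 1 and has no note about days 8 or 22. Section 3.1.6.5 says that second-course evaluations parallel the initial course.

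**The concern.** Safety and tolerability are part of the primary objective (Section 1.1.1), and Section 1.2.3.4 names neutropenia as the most notable serious toxicity. How often blood is counted decides which episodes are seen and how well their length is known. Length matters because Section 3.1.2.2.2 makes neutropenia dose-limiting only if it is grade 4 for 14 days or more, or if grade 4 febrile neutropenia occurs. Every subject has a first cycle, so the conflict is not confined to phase I.

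Table 1 does not settle it. Its weekly counts start once neutropenia has been seen, so a subject with a normal day 15 count has nothing further scheduled until day 29 under Section 3.4.4.

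**Working it through.** The plan gives no figure of its own on this point, so the check is calendar arithmetic on the two schedules.

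**Inputs.** Section 3.4.4 with 3.4.4.2 gives counts on days 1, 15, 29. Footnote 3 gives days 1, 8, 15, 22, 29. Dosing is "5mg PO daily for 21 days" (Section 3.1.3). The DLT threshold is 14 days of grade 4 (Section 3.1.2.2.2).

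**Gaps.** Section 3.4.4: 15 − 1 = 14 and 29 − 15 = 14. Footnote 3: 7 each. The longest episode that touches no count is the gap minus 1: 13 days against 6.

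**Episodes missed.** An episode of D days starting on day s covers days s to s + D − 1. Within a gap of g days it is unseen for max(0, g − D) start days. Onset on days 16 to 28 offers 13 start days, in one 14-day gap or two 7-day gaps. The documents give no episode lengths, so D is an assumption shown as a range.

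| D (days) | Unseen, Section 3.4.4 | Unseen, footnote 3 |
|---|---|---|
| 3 | 11 of 13 | 8 of 13 |
| 5 | 9 of 13 | 4 of 13 |
| 7 | 7 of 13 | 0 of 13 |
| 10 | 4 of 13 | 0 of 13 |
| 13 | 1 of 13 | 0 of 13 |
| 14 | 0 of 13 | 0 of 13 |

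**Dating the start of grade 4.** If grade 4 is first seen on day 29 and the previous scheduled count was not grade 4, onset could be any of days 16 to 29 under Section 3.4.4 (14 possible days), or any of days 23 to 29 under the footnote (7). Table 1 counts are weekly from then on, so the end is dated equally well under both.

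**Effect on a DLT call.** Suppose grade 4 starts between days 16 and 22, is present on day 36 and has gone by day 43. It lasts at least 36 − 22 + 1 = 15 days. With weekly counts after first detection, the footnote documents grade 4 on days 22, 29 and 36, a span of 36 − 22 = 14 days. Section 3.4.4 documents it on days 29 and 36, a span of 7. This assumes that duration is read from dated counts (no other method is given) and that the earlier Table 1 actions under the footnote do not shorten the episode. It shows what can happen, not how often.

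**Dosing.** A grade 4 count on day 8 would bring the Table 1 suspension up to 15 − 8 = 7 days before a first count on day 15. After day 15 the footnote's next count is day 22, when dosing has ended. Neither schedule has a count on days 16 to 21.

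**Timing.** The myeloma phase 1b study is reported "with the median time to grade 3/4 neutropenia in those experiencing this event being 3 weeks on therapy". That is day 21 or 22, which is 8 or 7 days before the next scheduled count under Section 3.4.4 and 1 or 0 days before it under the footnote.

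**The case against.** The best reply is that one footnote stands against the grid, Section 3.4.4 and Section 3.4.4.3.1, so this is a drafting slip with little effect. The plan accepts 14-day gaps elsewhere: footnote 3 itself gives day 15 only in cycles 2 and 3, and cycle 2 lies inside the 8-week DLT window. An afebrile episode short enough to pass unseen (13 days or less) is not a DLT, and one of 14 days or more always meets a count. Phase I is finished, with six subjects and no DLTs (Section 3.1.5).

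Much of this stands. It narrows the consequence but does not tell a site which schedule to follow.

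Stronger readings are tempting, and the documents do not support them:

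- *That day-15-only counting lets six extra doses (days 16 to 21) be taken during an unseen episode.* For onset after day 15, no scheduled count interrupts those doses under either version.
- *That the gap covers the time when neutropenia is expected in Kaposi sarcoma.* The 3-week median comes from relapsed or refractory myeloma on continuous dosing. Section 1.2.3.4 reports that solid-tumour patients tolerated substantially higher doses, and this trial doses in cycles. The figure is a rough guide to timing only.
- *That subjects were counted on different schedules, or that a phase I DLT was missed.* The documents do not say which schedule any subject had. Nothing in them shows mixed practice or a missed event.
- *That the second-course calendar contradicts Section 3.4.4.* It agrees with it. A question arises only through the statement that the courses run in parallel.

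**Conclusion.** The inconsistency is certain: footnote 3 cites Section 3.4.4 for a cycle 1 schedule that Section 3.4.4 does not contain. In size, it is a 14-day against a 7-day longest gap between scheduled cycle 1 counts, and a longest wholly unseen episode of 13 days against 6. Three effects follow: detection of short episodes, the precision with which the start of grade 4 is dated for the 14-day rule, and a possible earlier Table 1 action from a day 8 count. The conclusion does not extend to doses on days 16 to 21 or to the soundness of the completed dose decision.

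The gap arithmetic assumes counts on the scheduled days. It ignores unscheduled counts prompted by fever or symptoms and the rescheduling that Section 3.2.1.5 allows. The effect on reported neutropenia rates is plausible but cannot be measured from the documents.

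**What to change.** Reconcile footnote 3 of Section 3.4.1, Section 3.4.4 and Section 3.4.4.3.1 to a single cycle 1 schedule, and make the calendar grid show it. Which schedule applies is for the sponsor to decide. Then confirm that the second-course calendar in Section 3.4.2 matches it, given Section 3.1.6.5.

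When neutropenia incidence and duration are reported, state the count schedule actually used. If practice differed between subjects, record which schedule each one had.

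The cost is a short protocol correction and a sentence in the safety report, or one descriptive variable if practice was mixed. The reporting step is useful even if few first cycles remain. Footnote 3 and Section 3.4.4 already allow outside laboratories to do these checks for patients living at a distance.
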